2.1. Analysis Visit Windows and Periods

Because subjects do not always adhere to the protocol visit schedule, the following rules will be applied to assign actual visits (immunogenicity assessments) to analysis visits. The analysis visit windows and target days for each visit are displayed in

[Table 1](#). The reference day will be defined as:

- Day of first (Dose 1) vaccination if the actual visit occurs prior to the second (Dose 2) vaccination.
- Day of second (Dose 2) vaccination if the actual visit occurs after the second vaccination but prior to the third (Dose 3: only for subjects in the substudy) vaccination.

- Day of third (Dose 3: only for subjects in the substudy) vaccination if the actual visit occurs after the third vaccination.

Only the analysis time points and assays that are in scope for a specific statistical analysis (e.g. Interim Analysis, Final Analysis) are to be considered when assigning assessments to analysis visit windows. If a subject has 2 or more assessments within the same interval (analysis visit window), the one closest to the target day will be used for generating tables with descriptive statistics and graphical displays presenting data per time point. If 2 assessments are equidistant from the target day within the same interval, the latest assessment will be used. All assignments will be made in chronological order.

Because the analysis of adverse events (AEs) and laboratory abnormalities (except CD4+ cell counts in HIV-infected subjects) will be presented per period (and not per time point), these will be assigned to the analysis period and/or phase based on [Table 2](#). For CD4+ cell counts, the electronic case report form (eCRF) visit schedules will be used for the post baseline assessments. If only unscheduled visits are present for a time point, then the one closest to the scheduled visit will be used. If distances of multiple assessments to the scheduled visit are equal, the measurement with the latest date will be used. Similar to the CD4+ cell counts, the eCRF visits will also be used to present vital signs data of Cohort 3 subjects per time point.

Table 1: Analysis Visit Windows

Time Interval (Label on Output)	Time Interval PP ^a (Day)	Time Interval IG ^b (Day)	Target Time Point (Day)
Prior to Second (Dose 2) Vaccination			
Day 1 (Baseline)	≤ 1	≤ 1	1
Day 15 (14 days Post-dose 1)	[13; 17]	[2; 21]	15
Day 29 (28 days Post-dose 1)	[26; 32]	[22; 42]	29
Day 57 (56 days Post-dose 1)	[54; 60]	[43; 70]	57
Day 85 (84 days Post-dose 1)	[82; 88]	[71; 98]	85
Day 141 (140 days Post-dose 1)	NA	[99; 168]	-
Day 197 (196 days Post-dose 1)	NA	[169; 224]	-
Day 253 (252 days Post-dose 1)	NA	[225; 280]	-
≥Day 281 (≥280 days Post-dose 1) ^d	NA	≥281	-
Day 365 (364 days Post-dose 1)	[335; 395]	≥281	365
After Second (Dose 2) Vaccination but Prior to Third (Dose 3) Vaccination			
Day 36 (7 days Post-dose 2)	[6; 10]	[2; 15]	8
Day 64 (7 days Post-dose 2)			
Day 92 (7 days Post-dose 2)			
Day 148 (7 days Post-dose 2)	NA	[16; 101]	22
Day 204 (7 days Post-dose 2)			
Day 260 (7 days Post-dose 2)			
≥Day 289 (7 days Post-dose 2)			
Day 50 (21 days Post-dose 2)	[19; 25]		

Time Interval (Label on Output)	Time Interval PP ^a (Day)	Time Interval IG ^b (Day)	Target Time Point (Day)
Day 78 (21 days Post-dose 2)	NA		
Day 106 (21 days Post-dose 2)			
Day 162 (21 days Post-dose 2)			
Day 218 (21 days Post-dose 2)			
Day 274 (21 days Post-dose 2)			
≥Day 303 (21 days Post-dose 2)			
Day 209 (180 days Post-dose 2)	[166; 196]	[102; 196]	181
Day 237 (180 days Post-dose 2)			
Day 265 (180 days Post-dose 2)			
Day 321 (180 days Post-dose 2)	NA		
Day 377 (180 days Post-dose 2)			
Day 433 (180 days Post-dose 2)			
≥Day 462 (180 days Post-dose 2)			
Day 365 (364 days Post-dose 1) ^c	[335; 395]	≥222	365
Day 365 (Pre-dose 3) ^f	[335; 395]	≥365	-
After Third (Dose 3) Vaccination			
Day 369 (4 days Post-dose 3)	[4; 6]	[2; 6]	5
Day 372 (7 days Post-dose 3)	[6; 10]	[7; 15]	8
Day 386 (21 days Post-dose 3)	[19; 25]	[16; 101]	22
Day 545 (180 days Post-dose 3)	[166; 196]	[102; 273]	181
Day 730 (365 days Post-dose 3)	[335; 395]	≥274	365

^a The analysis based on the per protocol (PP) analysis set will be restricted to data points that fall within this window (ie, protocol-defined window).

^b The analysis based on the immunogenicity (IG) analysis set will be restricted to data points that fall within this window.

^c This analysis visit (Day 15) applies only to subjects in Groups 2 and 3 of Cohort 1.

^d This analysis visit is only applicable to the sensitivity analysis of subjects in Group G (ie, ≥281-day interval vaccination schedule) as shown in [Table 3](#) below. For the other analyses (ie, non-sensitivity), this will correspond to the Day 365 analysis visit.

^e For the windows after Dose 2 administration, only Day 365 (364 days Post-dose 1) window is taken with respect to the day of Dose 1 administration.

^f This analysis visit applies only to the subjects in the substudy (ie, Groups 1 and 2 subjects in Cohort 1 who received 3rd vaccination). For this visit, the assessment closest (but prior) to the vaccination should be used. If this visit coincides with the Day 365 (Day 365 Post-dose 1) visit, then the assessment should be assigned to both visits.

NA: Not applicable.

Note 1: The analysis windows and target days are based on the relative day (ie, with respect to the reference day [day of Dose 1, Dose 2 or Dose 3 administration]). The counting restarts from the day of a vaccination (ie, clock reset).

Note 2: Derivation of changes from pre-dose should be performed with respect to the reference value.

Time Interval (Label on Output)	Time Interval PP ^a (Day)	Time Interval IG ^b (Day)	Target Time Point (Day)
------------------------------------	--	--	----------------------------

Note 3: Immunogenicity sample collection at Day 141, Day 197, Day 253 and Day 281 visits were not planned according to the protocol. However, these visits were recorded for some Cohort 1 subjects due to the study pause (ie, late second [Dose 2] vaccination). If the analysis visit window contains the day of actual boost vaccination for these visits, then the assessment closest to the vaccination will be used.

Note 4: The same (ie, with respect to the number days since boost vaccination) post-boost visits are labeled differently. Day 36, Day 50 and Day 209 apply only to the 28-day interval schedule, Day 64, Day 78 and Day 237 apply to the 56-day interval schedule. Day 92, Day 106 and Day 265 apply only to the 84-day interval schedule. Day 148, Day 162 and Day 321 apply only to the 140-day interval schedule. Day 204, Day 218 and Day 377 apply only to the 196-day interval schedule. Day 260, Day 274 and Day 433 apply only to the 252-day interval schedule. \geq Day 289, \geq Day 303 and \geq Day 462 apply only to the \geq 281-day interval schedule.

Note 5: All assignments will be made in chronological order. Once an assessment is assigned to an analysis window, it will no longer be used for a later window.

Table 2: Analysis Periods

Phase	Period	Interval	
		From	To
Screening		00:00 on the date of signing the informed consent form	One minute prior to Dose 1 administration on Day 1
Regimen*	Post-dose 1	Date and time of Dose 1 administration	Minimum of: a) 23:59 on the date of last contact (for early study discontinuations) b) 23:59 on the date of relative Day 29 Post-dose 1 c) one minute prior to Dose 2 administration d) 23:59 on the date of database cut-off (in case of interim analysis)
Post-dose 1 FU		One minute after the end of the Post-dose 1 period	Minimum of: a) 23:59 on the date of last contact (for early study discontinuation or completion) b) one minute prior to Dose 2 administration c) 23:59 on the date of database cut-off (in case of interim analysis)
Regimen*	Post-dose 2	Date and time of Dose 2 administration	Minimum of: a) 23:59 on the date of last contact (for early study discontinuation or completion) b) 23:59 on the date of relative Day 29 Post-dose 2 c) 23:59 on the date of database cut-off (in case of interim analysis) Note: subjects who do not receive Dose 2 will not have a Post-dose 2 period.
Post-dose 2 FU		One minute after the end of the Post-dose 2 period	Minimum of: a) 23:59 on the date of database cut-off (in case of interim analysis) b) 23:59 on the date of last contact (for early study discontinuation or completion)
Regimen*	Post-dose 3	Date and time of Dose 3 administration	Minimum of: a) 23:59 on the date of last contact (for early study discontinuation or completion) b) 23:59 on the date of relative Day 29 Post-dose 3 c) 23:59 on the date of database cut-off (in case of interim analysis) Note: subjects who do not receive Dose 3 will not have a Post-dose 3 period.

Post-dose 3 FU		One minute after the end of the Post-dose 3 period	Minimum of: a) 23:59 on the date of database cut-off (in case of interim analysis) b) 23:59 on the date of last contact (for early study discontinuation or completion)
-------------------	--	--	---

Note 1: * Regimen period includes both the Post-dose 1, Post-dose 2 and Post-dose 3 periods.

Note 2: FU = follow-up.

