**Table 6: Visit Windows**

Visit Description	Day a	Window
Third Vaccination (12-15m pp)	3 rd Vaccination	
Four Days Post Third Vaccination	Day 5 Post 3 rd Vaccination	±1 days
Seven Days Post Third Vaccination	Day 8 Post 3 rd Vaccination	±2 days
Twenty-one Days Post Third Vaccination	Day 22 Post 3 rd Vaccination	±3 days
Follow-up 6 Months Post Third Vaccination	Day 180 Post 3 rd Vaccination	±15 days
Follow-up 1 Year Post Third Vaccination	Day 365 Post 3 rd Vaccination	±30 days

a The day of administration of the third vaccination is Day 1 of the substudy. Similarly, D2 Post 3rd vaccination is the second day of the substudy, ie, 1 day after the third vaccination.

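### Day 6 after the third vaccination is valid for both the 4-day and 7-day visits, so the SAP rules can report a compliant 7-day sample as the 4-day value or lose it

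*SAP*

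**What the plan says.** Protocol section 9.1.7, Table 6, counts the day of the third vaccination as Day 1. For the first of the two visits its row reads "Four Days Post Third Vaccination Day 5 Post 3 rd Vaccination ±1 days", which allows Days 4 to 6. For the second visit the row reads "Seven Days Post Third Vaccination Day 8 Post 3 rd Vaccination ±2 days", which allows Days 6 to 10.

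SAP section 2.1, Table 1, has the row "Day 369 (4 days Post-dose 3) [4; 6] [2; 6] 5", where the columns are the PP window, the IG window and the target day. The next row, beginning "Day 372 (7 days Post-dose 3", has PP window [6; 10], IG window [7; 15] and target Day 8. The footnotes restrict each analysis to data inside its own window and equate the PP windows with those of the protocol.

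Samples are placed by day relative to vaccination. When several fall in one window, the one nearest the target is used, and "If 2 assessments are equidistant from the target day within the same interval, the latest assessment will be used". SAP section 2.1 adds that "All assignments will be made in chronological order", and Note 5 to Table 1 bars an assessment already assigned to one window from a later one. eCRF visit labels are used only for CD4+ counts and Cohort 3 vital signs.

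**The concern.** A 7-day sample drawn on Day 6 complies with the protocol, yet the day-based rules consider it first for the 4-day visit. It can displace the true 4-day value, stand in for a missing one, or drop out of the summaries.

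Protocol section 3.2 describes a Phase 1 antibody rise of at least 10-fold within 7 days of a third dose, and the substudy is meant to confirm that profile. SAP section 6.2.1.3 plans geometric means, fold increases, responder rates and reverse cumulative distributions at 4 and 7 days post-dose 3. While antibody is climbing, a Day 6 value in the 4-day column tends to raise that summary, and the 7-day summary loses a valid value.

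The SAP handles comparable cases differently:

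- After Dose 2, a Day 6 sample counts as 7-day in both sets (PP [6; 10], IG [2; 15]).
- Where the Day 365 and pre-dose 3 visits coincide, footnote f assigns the sample to both.
- SAP Amendment 1 changed the 180-day post-boost IG window so that it would take in all PP data points. The 7-day post-dose 3 IG window does not meet that aim, because it excludes PP Day 6.

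**Working it through.** **Windows.** Target ± protocol allowance gives 5 ± 1 = [4; 6] and 8 ± 2 = [6; 10]. Both reproduce the PP windows in SAP Table 1. Their intersection is Day 6 only. The IG windows [2; 6] and [7; 15] do not overlap, and Day 6 lies wholly in the first.

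**Applying the rules to a 7-day sample drawn on Day 6**

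| 4-day sample | PP | IG |
|---|---|---|
| Day 4 | Distances to target 5 are 1 and 1, a tie. Day 6 is used as the 4-day value, Day 4 is dropped, 7-day is blank | Same |
| Day 5 | Day 5 is kept. Day 6 is lost if every sample in the window counts as assigned, and kept as the 7-day value if only the selected one does | Day 5 is kept, Day 6 is lost, 7-day is blank |
| Missing | Day 6 becomes the 4-day value, 7-day is blank | Same |
| Day 2 or 3 (outside the protocol window) | Day 6 becomes the 4-day value, 7-day is blank | Same: Day 6 is 1 day from target, against 3 or 2 |

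**Counting compliant pairs.** Take a 4-day sample on Day 4, 5 or 6 followed by a later 7-day sample on Days 6 to 10: 5 + 5 + 4 = 14 pairs. The pairs (4,6) and (5,6) fail, so 12 of 14 keep both visits correctly. In PP, under the lenient reading of Note 5, only (4,6) fails and 13 of 14 survive.

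**Size for a swapped subject.** Assume a 10-fold rise that is linear on the log scale over 7 days. A Day 6 value in place of a Day 4 value is then 10^(2/7) = 1.93 times too high. The documents give no values between vaccination and Day 8, so the true factor could be smaller or larger.

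**Size for the geometric mean.** If a fraction f of subjects is swapped, the 4-day geometric mean is multiplied by 1.93^f.

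- All 14 pairs equally likely (assumption), f = 1/14: 1.93^(1/14) = 1.05, a shift of (2/7)/14 = 0.020 log10.
- 5% to 10% of 7-day visits on Day 6 and one third of 4-day visits on Day 4 (assumptions), f = 1/60 to 1/30: factor 1.01 to 1.02.

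For scale, Protocol Table 10 uses SDs of 0.3 to 0.5 log10. With about 90 × 5/6 = 75 active subjects (assuming the 5:1 ratio holds in the substudy), the standard error is 0.3/√75 = 0.035 to 0.5/√75 = 0.058.

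**180-day row.** Table 6 gives Day 180 ± 15 = [165; 195]. SAP Table 1 has target 181 and PP window [166; 196], which is 181 ± 15. A compliant Day 165 sample is excluded and a Day 196 sample, outside Table 6, is admitted.

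**The case against.** The best defence is that the effect is small and confined. Post-dose 3 ELISA and VNA are exploratory, the substudy's secondary objective is safety, and no hypothesis is tested. Day 6 is nearer target 5 than target 8, and the protocol itself accepts Day 6 for a 4-day sample, so an IG boundary between Days 6 and 7 is defensible for samples of unknown intent. Day 6 may also be an uncommon choice for the 7-day visit: the diary runs for 7 days after vaccination and is completed on site at that visit (Protocol section 9.3.1). Unselected values should still appear in the data listing.

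Most of this stands and limits the importance of the point. It does not remove the defect. The intended visit is normally known, and the rules override it for a sample that met the protocol.

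A reader might go further than the documents allow in three ways:

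- **That every such Day 6 sample is lost to the 7-day visit.** In PP, with the 4-day sample on Day 5, this depends on whether Note 5 treats an unselected sample as assigned. The SAP does not say.
- **That about 20% of 7-day values are lost.** This takes Day 6 as 1 of 5 equally likely days. The documents give no distribution of visit days. Equal weight on the 14 pairs gives 2/14 = 14% (about 11 of 75), or 1/14 = 7% (about 5) in PP under the lenient reading.
- **That 4-day results are inflated 1.9-fold.** That factor applies to a swapped subject, not to the group mean.

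**Conclusion.** The point holds as a defect in the allocation rules. The pair (4,6) is misallocated with certainty in both sets, and so is a Day 6 sample when the 4-day sample is missing. The pair (5,6) loses its 7-day value with certainty in IG and ambiguously in PP, the set used for the primary immunogenicity analysis; two programmers could therefore produce different PP tables.

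The number of subjects affected cannot be derived from the documents. Under the assumptions shown, the shift in the 4-day geometric mean is about 1% to 5%, below one standard error and far too small to hide a 10-fold rise. The loss of valid 7-day values is the other cost. The primary safety endpoints and the 21-day post-boost ELISA endpoint are not affected.

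The one-day difference in the 180-day row is real but trivial. It does not follow that the SAP should simply adopt [165; 195]: target 181 is 180 days after a vaccination counted as Day 1 and matches the post-dose 2 row (Protocol Day 209 = 29 + 180).

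**What to change.** Add one sentence to SAP section 2.1 and a footnote to Table 1. In both PP and IG, a post-dose 3 sample labelled in the eCRF as the 4-day or 7-day visit is assigned to that visit when it lies inside that visit's protocol window; day-based windows apply only to other samples. For IG, this means a sample labelled 7-day is accepted on Day 6. All 14 compliant pairs then keep both visits, and Note 5 no longer decides the (5,6) case. The SAP already relies on eCRF visits for other data. There is no cost in data or subjects.

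Separately, reconcile the 180-day post-dose 3 PP window with Protocol Table 6, and state which day count applies.

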## COHORT 1 SUBSTUDY TIME AND EVENTS SCHEDULE

### Subjects at Selected Sites Receiving a Third Vaccination (Cohort 1, Groups 1-2)

Groups 1 & 2 b	Vaccination Phase and Post-vaccination Phase					Long-term Follow-up Phase a	
	1 Year Post Prime + 3 months	D2-D7 Post 3 rd Vaccination	D5 Post 3 rd Vaccination	D8 Post 3 rd Vaccination	D22 Post 3 rd Vaccination	D180 Post 3 rd Vaccination	D365 Post 3 rd Vaccination
Study procedures	3rd Vaccination		+4d p3v	+7d p3v	+21d p3v	+6m p3v	+1y p3v
Screening/Administrative							
Informed consent c	X						
Study vaccine administration	▲ d						
Safety assessments							
Urine pregnancy test e	X f						
Physical examination g	X f		X	X	X	X h	X h
Vital signs i	X f						
Distribution of subject diary	X						
Completion of diary at home j		X					
Review of diary by site staff				X			
Adverse events k	Continuous until 28 days after the third vaccination a,l						
Serious adverse events and immediate reportable events m	Continuous a,l						
Concomitant medications	X		X	X	X	X n	X n
Clinical Laboratory Assessments							
Chemistry, hematology (10 mL) o	X f			X			
Immunogenicity Assessments p							
Blood sampling (serum) for assessment of humoral immune responses (10 mL)	X f		X	X	X	X	X
Blood sampling (PBMC) for assessment of cellular immune responses (40 mL) q	X f				X		X
Approximate Blood Volumes with [without] PBMC r							
- By visit (mL) r Cohort 1 (Group 1 and 2)	60 [20]		10	20	50 [10]	10	50 [10]
- Cumulative (mL) r Cohort 1 (Group 1 and 2)	60 [20]		70 [30]	90 [50]	140 [60]	150 [70]	200 [80]

▲ Ad26.ZEBOV 5x10^7 vp or placebo

d p3v: days post third vaccination; m p3v: months post third vaccination; y p3v: year post third vaccination

**NOTE:** In case of early withdrawal from the study, early withdrawal assessments (ie, physical examination and immunogenicity assessments for serum) should be obtained. Subjects who wish to withdraw consent will be offered an optional visit for safety follow-up (before the formal withdrawal of consent); the subject has the right to refuse.

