**NOTE:** The day of administration of the third vaccination is Day 1 of the Cohort 1 substudy. Similarly, D2 Post 3rd vaccination is the second day of the Cohort 1 substudy, ie, 1 day after the third vaccination.

- a. All subjects will be followed up in a blinded manner by the site for the collection of serious adverse event information, immediate reportable events, and for blood draws for immunogenicity assessments until the last subject in that cohort has completed the study.
- b. Subjects eligible for the third vaccination are members of Cohort 1 (Groups 1 or 2) who consented to participate in the substudy. Approximately 90 subjects from Cohort 1 will be recruited at selected sites. For subjects who receive the third vaccination, the timings of the next post third vaccination visits will be determined relative to the actual day of the third vaccination.
- c. Informed consent form to enter in the Cohort 1 substudy must be provided and signed before the first substudy-related activity.
- d. After the third vaccination, subjects will remain at the site for a total of 30 ( $\pm 15$ ) minutes post-vaccination to monitor for the development of any acute reactions, or longer if deemed necessary by the investigator. Solicited and unsolicited adverse events emerging during the observation period at the site will be recorded in the case report form (CRF).
- e. Only for women of childbearing potential.
- f. Prior to study vaccine administration.
- g. An abbreviated, symptom-directed examination will be performed as indicated by the investigator.
- h. During the long-term follow-up, a physical examination should only be performed when related to serious adverse events and immediate reportable events.
- i. Includes blood pressure, pulse/heart rate (at rest) and body temperature.
- j. Subjects will use the subject diary to document solicited local and systemic adverse events (reactogenicity) in the evening after the third vaccination and then daily for the next 7 days at approximately the same time each day. Diaries should be completed at home by the subject. For illiterate subjects or those having difficulty completing the diary independently, the sites will make arrangements to have the diary completed according to their local practice.
- k. Non-serious adverse events will be reported until 28 days after the third vaccination. Pregnancies will be reported from signing of the informed consent form (ICF) until the end of the study.

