**Table 3: Visit Windows**

Visit Description	Day	Window
Seven Days Post-prime Vaccination	Day 8 for all groups	±2 days
Fourteen Days Post-prime Vaccination (only in Groups 2 and 3 from Cohort 1)	Day 15 for Group 2 and Group 3	±2 days
Boost Vaccination	Day 29 for Group 1 Day 57 for Group 2 Day 85 for Group 3	±3 days
Seven Days Post-boost Vaccination	Day 36 for Group 1 Day 64 for Group 2 Day 92 for Group 3	±2 days
Twenty-one Days Post-boost Vaccination	Day 50 for Group 1 Day 78 for Group 2 Day 106 for Group 3	±3 days
Forty-two Days Post-boost Vaccination	Day 71 for Group 1 Day 99 for Group 2 Day 127 for Group 3	±3 days
Follow-up 6 Months Post-boost a	Day 209 for Group 1 Day 237 for Group 2 Day 265 for Group 3	±15 days
Follow-up 1 Year Post-prime	Day 365 for all groups	±30 days

Refer to [Table 6](#) (Section 9.1.7) for the visit windows that will be allowed for the Cohort 1 substudy.

a Subjects who completed the 6-month post-prime visit (which has been replaced with the 6-month post-boost visit per protocol Amendment 2) prior to approval of Amendment 2 were required to also attend the 6-month post-boost visit after approval of Amendment 2.

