**Table 7: Whole Blood Volumes for Immunogenicity Assessments**

	Cohort	Humoral Immune Response (mL)	Cellular Immune Response (mL)	Approximate Total Blood Volume for Immunogenicity Assays (mL)
1	Healthy adult and elderly subjects	10	40	200 b /300/350 c
	Cohort 1 substudy subjects	10	40a	350d/360/400c,d/410c [430d/480/480c,d/530c]
2a	HIV-infected subjects	10	40	300
2b	Adolescents (12-17 years inclusive)	10	20	150
3	Children (4-11 years inclusive)			
	• 9-, 10- and 11-year old:	5	10	65
	• 6-, 7- and 8-year old:	2.5	6	36.5
	• 4- and 5-year old:	2.5	4	28.5

aThese samples are optional and may only be collected in a subset of subjects.

bOnly for subjects who do not receive a boost vaccination because of a study pause.

cSubjects in Groups 2 and 3 from Cohort 1 have an extra visit on Day 15, to assess the immune response after prime vaccination.

dIn case the pre-third vaccination blood sample coincides with the Day 365 blood sample.

\* Approximate total blood volumes including optional PBMC samples.

The immunologic assessments and purposes are summarized in [Table 8](#). The exploratory assay package may include, but might not be limited to, the listed assays.

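### The per-protocol window for the Pre-dose 3 sample in SAP Table 1 is the 1-year visit window, so it excludes the dosing-day sample of anyone given the third dose after Day 395

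*SAP*

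**What the plan says.** **SAP 2.1, Table 1.** The Day 365 (Pre-dose 3) row has a PP window of [335; 395], an immunogenicity-set (IG) window of ≥365, and no target day. The row above it, Day 365 (364 days Post-dose 1), has the same PP window. Three notes bear on the row:

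- Footnote a covers the whole PP column: "The analysis based on the per protocol (PP) analysis set will be restricted to data points that fall within this window (ie, protocol-defined window".
- Footnote f is written for this row: "For this visit, the assessment closest (but prior) to the vaccination should be used". It adds: "If this visit coincides with the Day 365 (Day 365 Post-dose 1) visit, then the assessment should be assigned to both visits".
- Note 5 says that a sample already placed in one window cannot serve a later one.

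**Protocol.** The substudy schedule times the third dose at "1 Year Post Prime + 3 months", and Table 6 lists it as "Third Vaccination (12-15m pp". A serum sample is due on the dosing day, footnoted "Prior to study vaccine administration". Table 7 treats a shared sample as one possible case: "In case the pre-third vaccination blood sample coincides with the Day 365 blood sample". The ±30-day window around Day 365 belongs to a different visit, "Follow-up 1 Year Post-prime", in Table 3.

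**SAP 2.3 and 6.2.** PP is the primary immunogenicity set. The substudy PP set has no limit on third-dose timing. A sensitivity analysis contrasts third doses given up to 30 days after Day 365 with later ones, so both kinds occurred. Fold increases from Pre-dose 3 are planned for the humoral and cellular assays.

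**The concern.** Footnote a describes [335; 395] as protocol-defined, but for this sample it is not: the protocol ties the sample to the third injection, which may come up to three months after the 1-year point. A programmer who follows footnote a will discard valid pre-injection samples that were collected on schedule, in subjects who remain in the PP set. Footnote f points to the sample one would want, but the SAP does not say whether it overrides the window or only chooses among samples inside it.

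The planned PP fold increase from Pre-dose 3 then depends on an unstated choice. The window also ends on the day where the timing sensitivity analysis splits the substudy. Any loss therefore falls on the late stratum only.

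**Working it through.** 1. **Reproduce the SAP windows.** Target day ± protocol window (Protocol Tables 3 and 6) gives the PP windows for the visits after Dose 3: 5 ± 1 = [4; 6]; 8 ± 2 = [6; 10]; 22 ± 3 = [19; 25]; 181 ± 15 = [166; 196] (SAP target day 181); 365 ± 30 = [335; 395]. For the Pre-dose 3 row, [335; 395] equals the Table 3 one-year visit, 365 ± 30. Table 6 gives the third dose a range of 12 to 15 months and no ± window.

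2. **Permitted dosing days, counted from Dose 1.** Take 12 months as Day 365 and 15 months as Day 365 + 91 = Day 456.
   - Permitted days: 456 − 365 + 1 = 92.
   - Days after 395: 456 − 395 = 61.
   - Share outside the PP window: 61/92 = 66%.
   - Other day-count conventions give 60/91 = 66% to 64/94 = 68%.
   - The 10-day postponement in Protocol 6.2 is not counted. With it: (61 + 10)/(92 + 10) = 71/102 = 70%.

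3. **Apply the notes to one case.** Third dose on Day 420, with a separate Day 365 sample and a dosing-day sample:

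| Reading | PP Pre-dose 3 value |
|---|---|
| Footnote a, with Note 5 | Missing: Day 420 is outside the window, and the Day 365 sample is already used by the row above |
| Footnote a first, footnote f choosing inside the window, Note 5 waived | Day 365 sample, 420 − 365 = 55 days old |
| Footnote f overrides the window | Day 420 sample |

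   The coincidence clause in footnote f does not help, because the two visits are separate. Under the second reading a sample taken exactly on Day 365 is 396 − 365 = 31 to 456 − 365 = 91 days old at dosing. Over the whole window the gap runs from 396 − 395 = 1 to 456 − 335 = 121 days.

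4. **IG set.** Counted from Dose 1, ≥365 includes all 92 permitted days, so late doses are not cut off.

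5. **Reference value.** SAP Section 2 defines the immunogenicity reference value by the boost date only, and Note 2 derives changes from pre-dose against it. Neither supplies a Pre-dose 3 value.

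**The case against.** The best defence is that footnote f already settles the row. It is the only rule written for this visit, the row has no target day for the generic closest-to-target rule to use, and a specific note normally prevails over a column-wide one. Late doses were plainly foreseen in Section 2.3, and the IG repeat would report a fold increase that includes them. The output is exploratory and descriptive. Protocol 3.2 cites Phase 1 antibody levels that were stable to 1 year and rose at least 10-fold after a third dose, so a somewhat older sample might change the fold increase little.

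Much of this stands. Footnote f is probably meant to govern, and the consequences are modest. But the SAP does not say that it governs, and footnote f works equally well as a choice among samples inside the window, which yields the older sample. The Phase 1 stability is not shown for months 12 to 15, and it does not help where the value is missing.

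A reader might go further and infer that the IG analysis and early Group 2 doses are lost too. Read literally, Note 1 and footnote e put this row on the Dose 2 clock. The IG limit would then be Day 365 + 28 = 393 in Group 1 and Day 365 + 56 = 421 in Group 2, which would exclude 28 and 56 of the 92 permitted days. That is an implausible intention. The row's label, the window it shares with the row above, and the labels that follow (Day 369 as 4 days after Dose 3) all point to Dose 1. The clock should be stated, but no loss is claimed on that reading.

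**Conclusion.** The stated PP window is wrong for this row, and its precedence relative to footnote f is not given. If footnote a governs, the dosing-day sample is excluded for every third dose after Day 395, which is 66% of permitted dosing days on the Dose 1 clock with 15 months taken as Day 456.

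That is a share of days, not of subjects. The documents do not say how many of the roughly 90 substudy participants were dosed late, so they support neither a claim that most participants lose the value nor any figure for lost precision.

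The effect is confined to exploratory PP fold increases from Pre-dose 3, and to the Day 395 contrast if it uses that measure, which Section 2.3 does not specify. Levels after Dose 3, responder rates and fold increases from Pre-dose 1 do not use the Pre-dose 3 value, and neither does the 21-day post-boost secondary endpoint. The SAP should be corrected. No view is taken on the timing of the third dose itself.

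**What to change.** For the Day 365 (Pre-dose 3) row in SAP Table 1:

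- state that days are counted from Dose 1;
- set the window, for both PP and IG, to run from Day 335 up to the Dose 3 injection;
- use the evaluable sample closest before the injection, as footnote f already says;
- state that footnote f takes precedence over Note 5 for this row.

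The Day 335 limit is needed so that, if later samples are missing, an earlier post-boost sample cannot become Pre-dose 3. The scheduled 6-month post-boost visit in Group 2 ends at Day 237 + 15 = 252, well below it.

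Extend the reference value in SAP Section 2, and Note 2, so that changes from Pre-dose 3 use this sample. Leave the Day 365 (364 days Post-dose 1) row as it is.

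The cost is SAP wording and a small derivation change. The pre-injection samples are already scheduled, so no new data are needed.
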